**Group 2:**

2. N=20 subjects aged 6-70 years will participate in the hybrid closed-loop phase in a remotely monitored 14-day outpatient environment
  - N=10 subjects aged 6-13.9 years
  - N=10 subjects aged 14-70 years

The first group of subjects (n=16) will commence the hybrid closed-loop phase in the hotel setting. On study day 3, subjects will transition to the outpatient setting for the remaining 12-days. After all subjects from the first group have completed the 2-day hotel phase, the second group of subjects may commence hybrid closed-loop. The second group of subjects (n=20) will use hybrid closed-loop in the outpatient setting for 14-days. It is anticipated that Group 1 will solely consist of existing Dexcom G6 users (those who were using the Dexcom G6 at the time of screening), while Group 2 will include some existing Dexcom G6 users and some non-Dexcom G6 users. Therefore, the primary safety and primary effectiveness endpoints will also be presented by Dexcom G6 use (users and non-users).

[figure not shown]
All subjects will participate in target BG challenges during the hybrid closed-loop phase. In total, all subjects will complete 14-days of closed-loop control, with approximately 72-hours spent at target blood glucose levels set to 130mg/dL, 140mg/dL and 150mg/dL, respectively.

After each subject in the prepivotal study has successfully completed 14-days of hybrid-closed-loop, they may immediately transition to and enroll in the pivotal study bypassing standard therapy (Phase 1) and continuing with the pivotal hybrid closed-loop phase (Phase 2). Remote monitoring will be discontinued as each subject enrolls in the pivotal study.

After 16-subjects from the prepivotal study have completed a minimum of 10-days on hybrid-closed-loop, the Data Safety Monitoring Board (DSMB) will convene and if the system is determined to be safe, the pivotal study may open enrollment to additional subjects for the hybrid closed-loop phase (Phase 2).

The standard therapy phase (Phase 1) of the pivotal study may commence in parallel to the prepivotal study. Figure 3 is a representation of the prepivotal transition into pivotal.

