## **Enrollment**

Subjects who meet all eligibility criteria and have completed all screening assessments will continue to enrollment. A subject is enrolled in the study upon placement of the first study CGM. Subjects that do not meet the eligibility criteria will not continue in the study and will be considered screen failures.

If for any reason a subject is no longer eligible for the study after the standard therapy phase has commenced but prior to the commencement of the hybrid closed-loop phase, the subject will not continue in the prepivot study. No additional study assessments will be required. The reason for study exit will be clearly documented.

## 8 STANDARD THERAPY - PHASE 1

The standard therapy phase will commence after all standard therapy assessments are completed per **Visit 2** – see Table 2: Schedule of Assessments.

During the standard therapy phase, subjects will be asked to perform the following:

- Manage their diabetes at home per their usual routine
- Administer meal boluses per their usual dosing routine
- Change their sensor if a sensor fails, or as needed
- Calibrate their CGM, if required, per the manufacturer's instructions
- Monitor their capillary blood glucose (BG) per usual routine
- Give meal boluses. The timing of the bolus delivery will be per each subject's typical dosing routine.

Extending standard therapy past 14-days will not constitute a protocol deviation unless standard therapy extends past 30-days. If subjects extend beyond the 14-days, the most recent 14-days of data will be used in the endpoint analysis if the data meets the criteria defined for CGM use and data availability. If a subject enrolls into the pivotal study, data collected in the standard therapy phase will be used in the endpoint analyses for the pivotal study as the subject will not be required to repeat the standard therapy phase as part of the pivotal study.

The standard therapy phase will be customized depending on the following subject profile:

- Current Dexcom G6 users
- Non-G6 users
- Pump Naïve users

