### Current Dexcom G6 Users

Current Dexcom G6 users will be required to participate in the assessments required as part of standard therapy but may be exempt from wearing the study CGM for 14-days if the following criteria are met:

- Willing to provide 14-days of CGM data from the past 30-days
- Meet the success criteria of 80% CGM use during any consecutive 14-days in the past 30-days
- Must have  $\geq 2,016$  CGM values during the 14-days

If exemption criteria are not met, subjects may choose to continue to collect data until they meet the criteria or will be required to participate in the entire 14-day standard therapy phase consistent with the requirements for non-G6 users.

Subjects deemed exempt from wearing the study CGM for 14-days will be eligible to immediately commence the hybrid closed-loop phase.

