Subjects will be provided, by the site, information regarding treatment of hypoglycemia and hyperglycemia including sick day management and emergency management of severe hypoglycemia and diabetic ketoacidosis. Subjects will be given contact information for study personnel and product support.

If a subject is on MDI, the investigator will advise the subject on the treatment regimen to reduce insulin depending on the insulin action profile of injected doses prior to the commencement of the hybrid closed-loop phase. MDI subjects will be required to keep a log to record daily doses of insulin during the standard therapy phase.

## 8.2 Visit 3

**Visit 3** will be conducted in person at the clinical study site one (1) day prior to the start of the hybrid closed-loop phase. All scheduled assessments will be performed according to Table 2: Schedule of Assessments. This visit will include assessment of whether subjects have met the CGM usage and data criteria.

Prior to the commencement of the hybrid closed-loop phase, subjects must meet the following criteria:

- At least 80% CGM use (11.2-days) during any consecutive 14-days in the past 30-days and
- $\geq 2,016$  CGM values during the 14-days

If the CGM criteria is not met, the standard therapy phase may be extended, per investigator discretion, or the subject may be withdrawn from the study. At the conclusion of the standard therapy phase, if the investigator determines that there have been no safety concerns, the subject will continue to the hybrid closed-loop phase. If the investigator determines that it is unsafe for the subject to continue into the hybrid closed-loop phase, the subject will not be allowed to continue in the second phase of the study, and the reason for study exit will be documented.

## 9 HYBRID CLOSED-LOOP - PHASE 2

The hybrid closed-loop phase will commence at **Visit 4** upon the conclusion of the standard therapy phase and after all assessments are performed according to Table 2: Schedule of Assessments.

During the hybrid closed-loop phase, subjects will be asked to do the following:

- Adjust pump and CGM parameters to optimize their insulin therapy in collaboration with the recommendations from the clinical study staff
- Follow their pre-exercise management such as insulin reduction for meal boluses, consumption of snacks, or adjusting their insulin delivery settings

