### **11.3.2 Reportable Adverse Events**

Adverse events will be assessed on an ongoing basis throughout the study. Adverse event reporting will begin at the start time of the standard therapy phase (i.e., insertion of the CGM sensor) and continue through the hybrid closed-loop phase until the subject's participation has ended. All adverse events must be followed until resolution, or until the AE has stabilized, or until the study has been completed.

Pre-existing medical conditions or symptoms observed prior to the start time of the standard therapy phase will not be recorded as an AE and should be collected in the subject's medical history. In the event there is a change (i.e., worsening) in the pre-existing medical condition or symptoms after enrollment meeting the criteria of a reportable adverse event, then an AE must be reported.

For this protocol, a reportable adverse event includes any untoward medical occurrence that meets one of the following criteria:

1. An SAE
2. An ADE unless excluded from reporting in Hypoglycemic Events and Hyperglycemic/Ketotic Events sections below
3. An AE occurring in association with a study procedure
4. An AE not related to a study device issue which leads to temporary or permanent discontinuation of the study device
5. An AE that affects the participant's ability to complete any study procedures
6. An AE for which a visit is made to a hospital emergency department
7. Hypoglycemic Events as defined below
8. Hyperglycemic/Ketotic Events as defined below.

Skin reactions from sensor or pod placement are only reportable if severe and/or required treatment.

For the purpose of this protocol, mild symptoms of hypoglycemia and hyperglycemia (i.e., clinically non-significant) or blood glucose values out of the normal range (whether or not they resulted in delayed meals or correction boluses) will not be reported as AEs unless determined to meet the reportable criteria in the Hypoglycemic Events and Hyperglycemic/Ketotic Events sections below.

All reportable AEs—whether volunteered by the participant, discovered by study personnel during questioning, or detected through physical examination, laboratory test, or other means—will be reported on an AE eCRF.

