### 5.4 ANALYSIS OF ADVERSE EVENTS

Safety summaries and analyses will be based on all subjects that are enrolled in the study (i.e., Intention to Treat analysis set). All adverse events reported over the course of the study will be summarized and tabulated by study phase (standard therapy or HCL), event category, seriousness, severity, and relationship to the study procedures and the investigational device. Except where indicated, a subject reporting the same adverse event more than once will be counted once when calculating the number and percentage of subjects with that particular event. Adverse Event outcomes will be assessed descriptively as opposed to inferentially.

Adverse events leading to death or to discontinuation from the study will be listed separately. A listing of all adverse events will be provided. No formal tests of hypotheses are proposed for the safety endpoints.

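### The by-phase adverse event table uses all enrolled subjects as its base, so exempt G6 users with little or no standard-therapy follow-up dilute the standard-therapy percentage

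*SAP*

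**What the plan says.** SAP 5.4 sets the base of the safety tables: "Safety summaries and analyses will be based on all subjects that are enrolled in the study". It then states the layout: "All adverse events reported over the course of the study will be summarized and tabulated by study phase (standard therapy or HCL"). A subject with repeats of the same event counts once in the number and percentage. Protocol 12.6.1 also tabulates by phase, and Protocol 12.8 makes unique subjects the default denominator. Neither document gives a denominator for each phase, or person-time.

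Protocol section 8 exempts current G6 users from the 14-day study sensor wear if they supply enough recent data of their own: "Subjects deemed exempt from wearing the study CGM for 14-days will be eligible to immediately commence the hybrid closed-loop phase". Table 2, footnote i, lets them skip ST2 (Visit 3).

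On how many this could be, Protocol 5.2 says: "It is anticipated that Group 1 will solely consist of existing Dexcom G6 users". Group 1 has 16 of the 36 planned subjects. Group 2 is to contain an unspecified number of G6 users.

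Protocol 11.3.2 fixes when observation starts: "Adverse event reporting will begin at the start time of the standard therapy phase (i.e., insertion of the CGM sensor").

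For subjects who become ineligible after ST starts but before HCL, the Enrollment text in section 7.1 says: "No additional study assessments will be required".

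**The concern.** A percentage of subjects with an event is interpretable only if everyone in the denominator was observed for a comparable time. In the HCL column each entrant is scheduled for 14 days. In the ST column an exempt G6 user may have close to zero days, because that user's ST glucose record predates the study and carries no adverse event collection. Such a user counts as event-free when in fact unobserved.

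The start of observation is also unclear for these users. Reporting begins at sensor insertion, and an exempt user may have no study sensor inserted during ST.

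In a single-arm study the ST column is the only internal reference for event frequency. Readers will compare it with the HCL column whether or not a test is planned. From the planned table they could not tell how much of a difference comes from the denominator.

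**Working it through.** The plan states no event rate or exposure total, so there is no figure of its own to reproduce. The group sizes do reconcile: 16 + 20 = 36, and 8 + 10 = 18 per age cohort.

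**Inputs from the documents:** 14 days per phase; 36 evaluable subjects; up to 48 enrolled; Group 1 = 16, Group 2 = 20.

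**Assumptions:** *e* exempt subjects with no ST follow-up (the documents give no count); *N* enrolled; *H* entering HCL; the same true 14-day event probability *p* in both phases; anyone leaving before HCL was non-exempt and followed for the full 14 ST days.

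**Formulas:**
- Followed in ST: *F* = *N* − *e*
- Expected ST percentage as planned: *p* × *F*/*N*
- Expected HCL percentage as planned: *p* × *H*/*N*
- Apparent HCL/ST ratio when the truth is 1: *H*/*F*
- Person-days: 14*F* and 14*H*

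| *N* | *e* | *F* | *H* | ST / HCL person-days | ST shown as share of *p* | HCL shown as share of *p* | Apparent ratio |
|---|---|---|---|---|---|---|---|
| 36 | 0 | 36 | 36 | 504 / 504 | 100% | 100% | 1.00 |
| 36 | 8 | 28 | 36 | 392 / 504 | 78% | 100% | 1.29 |
| 36 | 16 | 20 | 36 | 280 / 504 | 56% | 100% | 1.80 |
| 36 | 26 | 10 | 36 | 140 / 504 | 28% | 100% | 3.60 |
| 48 | 16 | 32 | 36 | 448 / 504 | 67% | 75% | 1.13 |
| 48 | 26 | 22 | 36 | 308 / 504 | 46% | 75% | 1.64 |

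For illustration, with *p* = 10%, *N* = 36 and *e* = 16, the ST column would show 10% × 20/36 = 5.6% and the HCL column 10%. Among the 20 subjects followed in ST, the expected figure is 10%.

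**Sensitivity to the zero-day assumption.** One ST day for each of 16 exempt subjects gives 280 + 16 = 296 person-days, or 296/504 = 59% of HCL exposure.

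**Sensitivity to ST length.** Protocol section 8 allows ST to run to 30 days without a deviation. If all 20 followed subjects ran to 30 days, ST exposure would be 20 × 30 = 600 person-days, above the 504 in HCL. The two are equal at a mean ST length of 504/20 = 25.2 days.

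**The case against.** The strongest reply is that nothing formal rests on this column. SAP 5.4 makes the adverse event analysis descriptive and provides a full listing. The primary and secondary safety endpoints are restricted to HCL (SAP 3.1), with mITT as their primary set (SAP 7.1.2). Protocol 11.7.2 has the DSMB compare severe hypoglycemia and DKA with published registry rates. This stands. A reader might infer that the DSMB would be misled by an apparent rise on the device, but no stated DSMB rule uses the ST column.

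A reader might also infer that the ST column is driven toward zero, or that a 1.8- or 3.6-fold artefact should be expected. The documents do not support either. Those ratios need every enrolled subject to enter HCL and no ST extension. Subjects who leave before HCL dilute the HCL column too, which brings 1.80 down to 36/32 = 1.13 in the 48-enrolled case. Exemption also depends on meeting the sensor data criteria, so even 16 is not certain. Nor is an equal true rate a natural expectation, because investigational-device effects can arise only once the system is worn.

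A third tempting inference is that ST events are lost because Visit 3 does not ask about them. Protocol 8.2 describes that visit only in these terms: "This visit will include assessment of whether subjects have met the CGM usage and data criteria". But Visit 4 follows one day later and assesses adverse events before HCL treatment starts (9.3). Reporting is ongoing throughout the study (11.3.2), and 8.2 makes progression depend on the investigator finding no safety concerns. For subjects who continue, the enquiry moves by about a day.

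Last, the exit wording in 7.1 does not by itself show that leavers go unassessed. Table 2, footnote a, and section 9.9 provide an early-withdrawal visit that includes adverse events. The problem is that these places conflict.

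None of these replies supplies a denominator or an exposure figure for the ST column.

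**Conclusion.** The concern holds in a limited form. Under SAP 5.4 as written, the ST percentage is multiplied by the fraction of enrolled subjects actually followed in ST. That factor is 20/36 = 56% if 36 enrol, all enter HCL and all 16 of Group 1 are exempt with no ST time. It moves with the exempt count, the losses before HCL and the length of ST, and in some combinations the exposure imbalance reverses. The planned table does not show any of these quantities, so its reader cannot judge the size of the effect.

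The consequence is a by-phase table that cannot be read across its columns. It does not put a safety endpoint or a stopping decision in error.

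**What to change.** 1. In SAP 5.4, make the denominator of each phase column the subjects prospectively followed in that phase, and print that number in the column head.
2. Report person-days and events per person-time for each phase.
3. State when ST adverse event follow-up begins for exempt G6 users, or that they contribute none.
4. Reconcile the Enrollment text in Protocol 7.1 with Table 2, footnote a, and section 9.9, so that it is clear whether subjects leaving between ST and HCL have an adverse event enquiry and when their follow-up ends.

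An adverse event line at Visit 3 is optional, since Visit 4 already asks before HCL begins.

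The cost is SAP wording, a follow-up start and end date per subject and phase, and one protocol clarification. The ST column will have a smaller denominator and a wider margin of error: with 20 subjects instead of 36, the standard error of a given percentage is √(36/20) = 1.34 times as large. That width reflects the information the design collects. Rates per person-time will not remove differences in how closely subjects are watched, because remote alerts run only in HCL (Protocol 3.1); a table footnote should say so.

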### 5.5 EVALUATION OF DEVICE DEFICIENCIES

Device deficiencies will be tabulated and listed in a manner similar to the methods described for adverse events. Any device deficiency leading to an adverse event or study termination will be listed separately.

## 6 ANALYSIS OF SECONDARY EFFECTIVENESS ENDPOINTS

The secondary effectiveness objective is to evaluate additional glycemic measures of effectiveness of the Omnipod Horizon™ Automated Glucose Control System. The secondary effectiveness objective will be evaluated based on the following per subject endpoints:

- Glucose metrics from system CGM during the hybrid closed-loop phase will be compared to the standard therapy phase during the day, overnight, and overall:
  - Mean glucose
  - Percentage of time in range 70-180 mg/dL
  - Percentage of time in range 70-140 mg/dL
  - Percentage of time in range > 180 mg/dL
  - Percentage of time in range  $\geq$  250 mg/dL
  - Percentage of time in range  $\geq$  300 mg/dL
  - Percentage of time in range < 70 mg/dL
  - Percentage of time in range < 54 mg/dL
  - Standard deviation
  - Coefficient of variation

## Statistical Analysis Plan

- Glucose management indicator (GMI) based on overall mean glucose
- Percentage of time in hybrid closed-loop as proportion of overall device usage time
- Insulin requirements during the hybrid closed-loop phase will be compared to the standard therapy phase:
  - Total daily insulin (TDI) (units, units/kg)
  - Total daily basal insulin (units, units/kg)
  - Total daily bolus insulin (units, units/kg)

### 6.1 ANALYSIS OF PERCENTAGE OF TIME IN RANGE ENDPOINTS

The analysis of secondary endpoints that summarize the percentage of time in range (TIR) will follow the analysis set forth for the primary effectiveness endpoint, with the range value updated as appropriate.

### 6.2 ANALYSIS OF PERCENTAGE OF TIME IN HYBRID CLOSED-LOOP

The percentage of time in hybrid closed-loop will be calculated as:

$$100 \times \frac{\text{sum of gaps between consecutive CGM records}}{\text{difference between the earliest and the latest CGM records}} = \% \text{ time in HCL}$$

A gap is calculated as the difference in time (either minutes or seconds) between two consecutive CGM records as captured by the Horizon™ System. The gaps are then summed to obtain total time in HCL. As records are generally taken in about every 5 minutes and to ensure that only confirmed HCL records are included, gaps greater than 7 minutes will be excluded from analysis. For the denominator, the chronologically earliest and the latest CGM records during HCL as captured by the Horizon™ System will be used.

As opposed to the time in range endpoints, records with no glucose value in the Horizon™ System device output (such as due to an error or device deficiency during which the device does not record glucose readings) will be included in analysis. CGM records reported prior to start of HCL or after subject's discontinuation from HCL will be excluded from analysis. This endpoint will also be reported separately for the manual and automated modes.

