#### **2.3 STUDY SCHEDULE**

The study will consist of 14-day standard therapy (ST) phase and a 14-day hybrid closed-loop (HCL) phase. Following the ST phase, subjects will be divided into 2 groups. Group 1 subjects (N=16; 8 subjects in each age cohort) will participate in the HCL phase for the first 2 days while in the supervised hotel/rental house environment and then transition to the 12-day outpatient setting. The Group 2 subjects (n=20; 10 subjects in each age cohort) will participate in the HCL phase in a 14-day outpatient setting.

The Horizon™ System has two modes. In manual mode, the system will function equivalently to

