### 3.3 SECONDARY EFFECTIVENESS OBJECTIVE AND ENDPOINTS

The secondary effectiveness objective is to evaluate additional glycemic measures of effectiveness of the Omnipod Horizon™ Automated Glucose Control System. The secondary objective will be evaluated based on the following per subject endpoints:

- Glucose metrics from system CGM during the hybrid closed-loop phase will be compared to the standard therapy phase during the day, overnight, and overall:
  - Mean glucose
  - Percentage of time in range 70-180 mg/dL
  - Percentage of time in range 70-140 mg/dL
  - Percentage of time in range > 180 mg/dL
  - Percentage of time in range  $\geq$  250 mg/dL
  - Percentage of time in range  $\geq$  300 mg/dL
  - Percentage of time in range < 70 mg/dL
  - Percentage of time in range < 54 mg/dL
  - Standard deviation
  - Coefficient of variation
- Glucose management indicator (GMI) based on overall mean glucose
- Percentage of time in hybrid closed-loop as proportion of overall device usage time
- Insulin requirements during the hybrid closed-loop phase will be compared to the standard therapy phase:
  - Total daily insulin (TDI) (units, units/kg)
  - Total daily basal insulin (units, units/kg)
  - Total daily bolus insulin (units, units/kg)

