### 6.5 ANALYSIS OF SECONDARY EFFECTIVENESS ENDPOINTS

There are no pre-specified hypotheses associated with the secondary effectiveness endpoints. Summary statistics will be presented by age cohort for all endpoints, stratified by time points of interest (e.g., day, night, overall). All statistical comparisons will be conducted at a two-sided significance level of 5%. If the assumptions for parametric tests are grossly violated, a non-parametric method such as Wilcoxon signed rank test may be used. Since the results of endpoint analyses will not be used to support clinical claims, no adjustment for multiplicity will be performed.

As described in this document, results will be stratified by phase of the study (ST versus HCL), age group (subjects aged 6-13.9 years versus subjects aged 14-70 years) and day versus night (daytime: 6AM to <12AM; nighttime as 12AM to <6AM). Results for other subgroups may be presented as appropriate.

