### 7.1.3 Per Protocol

The Per-Protocol (PP) analysis set is a subset of the mITT analysis set. Subjects will be included in the PP analysis set if they have a minimum of 80% system use during the hybrid closed-loop phase inclusive of manual and automated modes over a duration of 14 days and have completed the study without major protocol deviations. The PP analysis set will be used as supportive analysis for the effectiveness endpoints. The following will be considered major protocol deviations:

- Major inclusion/exclusion criterion deviation
- Significant protocol non-compliance that may confound the study objective data (e.g., use of prohibited medications)

The list of subjects excluded from the PP analysis set will be determined prior to analysis. If the PP analysis set does not differ from the mITT analysis set, separate analyses will not be presented.

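### The pooled percentage of time in hybrid closed-loop in SAP 6.2 has no mode condition, so where CGM records continue in Manual Mode it measures record coverage, not the named endpoint

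*SAP*

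**What the plan says.** SAP 3.3 and SAP 6 list this secondary effectiveness endpoint: "Percentage of time in hybrid closed-loop as proportion of overall device usage time". The protocol lists it in the same terms (6.3.1, 12.1.4) and gives no formula.

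SAP 6.2 supplies the formula.

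- **Numerator.** Time differences between successive CGM records captured by the system: "The gaps are then summed to obtain total time in HCL". Records without a glucose value count.
- **Filter.** Records come about every 5 minutes, and "to ensure that only confirmed HCL records are included, gaps greater than 7 minutes will be excluded from analysis".
- **Denominator.** "For the denominator, the chronologically earliest and the latest CGM records during HCL" are used.
- **By mode.** "This endpoint will also be reported separately for the manual and automated modes". No separate formula or denominator is given for the by-mode figures.

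The term HCL has two uses. In the SAP it names the phase: "The study will consist of 14-day standard therapy (ST) phase and a 14-day hybrid closed-loop (HCL) phase". Protocol 2.1.1 uses hybrid closed-loop as the gloss for Automated Mode. SAP 2.3 says that the system has both a manual and an automated mode, and the per-protocol rule in SAP 7.1.3 asks for a "minimum of 80% system use during the hybrid closed-loop phase inclusive of manual and automated modes", so both modes are expected within the phase.

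**The concern.** The endpoint name asks how much of device use was closed-loop. To answer that, the numerator must separate closed-loop time from other time. The formula does not do so. The 7-minute rule is given as the safeguard that keeps only confirmed closed-loop records, but it tests the spacing of records. Two Manual Mode records 5 minutes apart pass it.

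At stake is the meaning of one reported result. A reader of the study report would take a percentage of time in hybrid closed-loop close to 100 as evidence that subjects stayed in Automated Mode. Under this formula the same value would appear for a subject who spent much of the phase in Manual Mode with the sensor recording.

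**Working it through.** The documents state no value for this endpoint, so there is no planned figure to reproduce. The check applies the SAP 6.2 formula literally to constructed records.

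**Do records continue in Manual Mode?** Protocol 2.1.1 says the controller can use sensor glucose in Manual Mode, acting as a sensor-augmented pump. Protocol 13.2.1 stores every CGM reading of the phase, without a mode limit. SAP 6.2 plans a manual-mode figure, which this formula can yield only if such records exist. Records in Manual Mode are therefore likely, though not stated outright.

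**Inputs.** From the documents: 14 days, records about every 5 minutes, 7-minute cut-off. Assumed: the Manual Mode time per day and the pattern of record loss. 14 × 288 = 4,032 intervals of 5 minutes, or 1,440 minutes per day.

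**Formulas.**

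- Pooled (SAP 6.2) = 100 × (all intervals ≤ 7 min) / (first-to-last span)
- Automated-only = 100 × (intervals ≤ 7 min in Automated Mode) / (same span)

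**Complete records.** Every interval is 5 minutes, so the pooled figure is 1,440/1,440 = 100% each day.

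| Manual min/day | Manual share | Pooled | Automated-only |
|---|---|---|---|
| 0 | 0% | 100.0% | 100.0% |
| 70 | 70/1,440 = 4.9% | 100.0% | 95.1% |
| 145 | 145/1,440 = 10.1% | 100.0% | 89.9% |
| 360 | 360/1,440 = 25.0% | 100.0% | 75.0% |

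The excess of the pooled figure equals the manual share. A second run, with one manual block in mid-phase, gave 100% at every manual share from 0% to 100%. With about 4.4% of time lost to record gaps, the pooled figure stayed at 95.59% throughout, while the automated-only figure fell from 95.59% (no manual time) to 76.84% (20% manual) and 47.07% (50% manual).

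**No records in Manual Mode.** At 25% manual, each manual block becomes one long interval and drops out of the numerator but stays in the span. The pooled figure is then 75.0%, the automated share, and the defect does not arise.

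**Choice of denominator under record loss.** True split 1,080 automated and 360 manual minutes per day (75/25); 145 minutes per day lost (10.1%), leaving 1,295 recorded. Pooled = 1,295/1,440 = 89.9% in every row.

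| Where the loss falls | Recorded auto / manual (min) | Auto / manual over span (÷1,440) | Auto / manual over recorded time (÷1,295) |
|---|---|---|---|
| Both modes | 970 / 325 | 67.4 / 22.6% | 74.9 / 25.1% |
| Automated only | 935 / 360 | 64.9 / 25.0% | 72.2 / 27.8% |
| Manual only | 1,080 / 215 | 75.0 / 14.9% | 83.4 / 16.6% |

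Neither denominator is right in all three cases. The span never puts the automated share above the true 75%. Recorded time does so when the loss falls in Manual Mode (83.4%), and it reads 100% if Manual Mode produces no records at all.

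**Intervals at a mode switch.** Complete records, 25% manual. Assigned to the mode at the start of the interval, the shares are 75.0/25.0%. If left unassigned, one manual block per day loses 28 × 5 = 140 of 20,160 minutes (0.7 points in total), and four blocks per day lose 112 × 5 = 560 minutes (2.8 points).

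**The case against.** The strongest reply is that the planned outputs already contain the answer. If the automated-mode figure takes the denominator given in the same section, it is automated time over device time, which is the named endpoint. With complete records it is exact at every share tested. This stands, and it is the main reason the harm is small. It does not remove the problem: the by-mode figures are an addition, the pooled figure still carries the endpoint name, and the SAP does not state the by-mode denominator.

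A second reply is that HCL in the SAP means the phase, and SAP 1 gives the SAP precedence over the protocol. On that reading the formula is a coherent measure of recorded use during the phase. It is then still not the endpoint. Both documents name the endpoint in the same words, so precedence has nothing to settle, and a measure that ignores mode cannot be closed-loop time as a share of device use. A reader might go further and treat the pooled figure as the system-use measure of SAP 7.1.3. The documents do not support that, because SAP 7.1.3 gives no formula.

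A reader might also infer that the denominator must change to recorded usage time. That does not follow. The first-to-last span is a natural reading of overall device usage time, and the loss scenarios show a trade-off, with recorded time able to overstate closed-loop use.

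Finally, the 100% result is an identity of a formula without a mode term. It shows what the figure cannot detect, not how far it will be off in this study.

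**Conclusion.** The point holds as a minor correction. Where CGM records continue in Manual Mode, the pooled figure in SAP 6.2 is record coverage in both modes and does not respond to the Manual Mode share. It exceeds the automated share over the same span by the recorded manual share: 25.0 points in the assumed 75/25 case with complete records.

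This rests on one condition that the documents make likely but do not state, namely that records continue in Manual Mode, and on assumed manual shares. A reader might infer that reported closed-loop use will be materially overstated. The documents do not support that: they give no expected manual share, and it could be close to zero.

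The consequence is limited. "There are no pre-specified hypotheses associated with the secondary effectiveness endpoints", SAP 6.5 says the results support no clinical claim, SAP 2.5 sets no success criterion, and the primary time-in-range and safety endpoints do not use this formula.

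**What to change.** In SAP 6.2:

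1. Restrict the headline numerator to intervals of 7 minutes or less in Automated Mode, and keep the existing first-to-last-record denominator for the hybrid closed-loop phase.
2. State that both by-mode figures use that same denominator, and assign an interval at a mode switch to the mode at its start.
3. Keep the present pooled figure alongside, renamed *CGM record coverage* or *system use*. The first name avoids confusion with the per-protocol criterion, for which no formula is given.

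The cost is SAP text and one formula. No new data are needed: SAP 6.2 already plans figures by mode, and Protocol 3 lists time spent in each mode among the data portal outputs. The downside is a lower headline for subjects with Manual Mode time. Automated Mode records lost within the span lower it further (64.9% against a true 75% if 10.1% of time is lost, all in Automated Mode). The coverage figure beside it shows the amount of that loss, though not the mode in which it fell.
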